## 7.5. Dosing and Number of Cycles in the Study

The number of cycles of treatment received will be summarized by reason off treatment for all subjects evaluable for toxicity by treatment arm. The following rule will be applied: subjects who start treatment but discontinue during Cycle 1 will be reported for “reason off treatment” in Cycle 1; subjects who discontinue during Cycle 5 (for example) will be counted as “Completed Treatment” for cycles 1, 2 , 3, and 4 and under reason off treatment for Cycle 5.

Dose during Induction and during Continuation phase will be summarized as a continuous variable. Dose during a phase is computed as the average dose across all days when medication was taken (dosing interval). Dosing interval is the interval between the date of the first dose in the phase till the last dose date recorded in the diary. If during the dosing interval, dose modification indicates missed or dose withdrawn, the respective days are be counted with 0 mg.

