5.3 Dose Modifications and Toxicity Management

5.3.1 Dose Modifications General Guidelines for Everolimus/Placebo

CTCAE term (AE description) and grade: The descriptions and grading scales found in the revised NCI Common Terminology Criteria for Adverse Events (CTCAE) Version 4.0 will be utilized for AE reporting. All appropriate treatment areas should have access to a copy of the CTCAE Version 4.0. A copy of the CTCAE Version 4.0 can be downloaded from the CTEP web site (<http://ctep.cancer.gov>).

All appropriate treatment areas should have access to a copy of the CTEP CTCAE Version 4.0. (see Appendix E).

Dose modifications for all drugs will be made using the general guidelines below.

- All dose reductions are permanent. Fulvestrant will not be dose reduced.
- Regardless of the reason for holding any study drug treatment, the maximum allowable length of treatment interruption is \leq 3 weeks. If the delivery of any study drug due to toxicity is delayed for more than 3 weeks, that drug should be permanently discontinued.
- No more than 2 dose reductions for everolimus/placebo will be allowed. Further need for dose reduction will result in discontinuation of that drug.
- If dose is delayed due to toxicity, labs/toxicity should be reevaluated at least weekly until recovery to treatment levels, or as indicated in the dose modification tables.
- Patients who discontinue everolimus/placebo because of suspected everolimus-associated toxicity should continue treatment with fulvestrant alone until disease progression.
- In unusual circumstances where fulvestrant must be discontinued prior to disease progression due to intolerable fulvestrant-associated toxicity, the Medical Monitor should be contacted.

Table 5-0

Everolimus or Placebo Dose Level Modification Guidelines

	Everolimus/Placebo	Fulvestrant
Starting dose	10 mg daily (two- 5 mg tablets)	500 mg
Dose Level -1	5 mg daily	No reduction
Dose Level -2	5 mg every other day	No reduction

Table 5-1**Non-Hematological Criteria for Dose-Modification in Case of Suspected Everolimus or Placebo Related Adverse Events and Re-Initiation of Everolimus or Placebo Treatment**

Adverse Event	Action
Non Hematological	
Reactivation of HBV or HCV flare	Please refer to Table 5-4 and Table 5-5.
Non-Infectious Pneumonitis	Please refer to Table 5-6.
AST or ALT elevation Grade 1 (>ULN - 3.0x ULN) Grade 2 (>3.0 - 5.0x ULN)	Maintain current dose level.

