5.3.2 Common Adverse Events Associated with Everolimus

The data described below reflect exposure to everolimus (n=274) and placebo (n=137) in a randomized Phase III study for the treatment of metastatic renal cell carcinoma. In total, 165 patients were exposed to everolimus 10 mg/day for \geq 4 months. The median age of patients was 61 years (range 27 to 85). The most common adverse reactions (incidence \geq 10%) were stomatitis, rash, fatigue, asthenia, diarrhea, anorexia, nausea, mucosal inflammation, vomiting, cough, peripheral edema, infections, dry skin, epistaxis, pruritus, and dyspnea. The most common grade 3-4 adverse reactions (incidence \geq 2%) were infections, stomatitis, fatigue, and pneumonitis.

The median duration of blinded study treatment was 141 days (range 19 to 451) for patients receiving everolimus and 60 days (range 21 to 295) for those receiving placebo. The rates of treatment-emergent adverse reactions resulting in permanent discontinuation were 7% and 0% for the everolimus and placebo treatment groups, respectively. Most treatment-emergent adverse reactions were grade 1 or 2 in severity. Grade 3 or 4 treatment-emergent adverse reactions were reported in 39% versus 7% of patients receiving everolimus and placebo, respectively. Deaths due to acute respiratory failure (0.7%), infection (0.7%), and acute renal failure (0.4%) were observed on the everolimus arm.

Everolimus has immunosuppressive properties and may predispose patients to bacterial, fungal, viral or protozoan infections, including infections with opportunistic pathogens. Localized and systemic infections, including pneumonia, other bacterial infections, invasive fungal infections, such as aspergillosis or candidiasis and viral infections including reactivation of hepatitis B virus, have been described in patients taking everolimus. Some of these infections have been severe (e.g. leading to respiratory or hepatic failure) and occasionally have had a fatal outcome.

Physicians and patients should be aware of the increased risk of infection with everolimus. Treat pre-existing infections prior to starting treatment with everolimus. While taking everolimus, be vigilant for symptoms and signs of infection; if a diagnosis of infection is made, institute appropriate treatment promptly and consider interruption or discontinuation of everolimus. If a diagnosis of invasive systemic fungal infection is made, discontinue everolimus and treat with appropriate antifungal therapy.

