Grade 3	CT scan with lung windows and pulmonary function testing includes: spirometry, DLCO, and room air O ₂ saturation at rest. Monitoring at each visit until return to ≤ grade 1. Return to initial monitoring frequency if no recurrence. Bronchoscopy with biopsy and/or BAL is recommended.	Consider corticosteroids if infective origin is ruled out. Taper as medically indicated.	Rule out infection and interrupt everolimus until symptoms improve to Grade ≤ 1. Consider re-initiating everolimus at one dose level lower. Discontinue everolimus if failure to recover within ≤ 21 days.
Grade 4	CT scan with lung windows and required pulmonary function testing, if possible, includes: spirometry, DLCO, and room air O ₂ saturation at rest. Monitoring at each visit until return to ≤ grade 1. Return to initial monitoring frequency if no recurrence. Bronchoscopy with biopsy and/or BAL is recommended if possible.	Consider corticosteroids if infective origin is ruled out. Taper as medically indicated.	Rule out infection and discontinue everolimus.

All interruptions or changes to study drug administration must be recorded.

It will be documented whether or not each patient completed the clinical study. If for any patient either study treatment or observations were discontinued the reason will be recorded.

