j: Adverse events related to fulvestrant and/or everolimus/placebo will be followed for 30 days after the last dose of study therapy (fulvestrant and/or everolimus/placebo) or until ≤ grade 1 or if the grade is >1, the event must be permanent and stable. Please note- Serious adverse events >30 days after last dose of fulvestrant and/or everolimus/placebo are not reported unless the event may be related to everolimus/placebo.

k: CBC and chemistry may be used to assess ongoing toxicity but are not required in the Continuation Phase for patients who receive fulvestrant alone. Patients who continue fulvestrant with everolimus should periodically have CBC, chemistries, fasting glucose, fasting lipids, HBV DNA, HCV RNA-PCR per labeling guidelines.

l: Study Drug Compliance (Pill Diary) for those patients who receive everolimus in the Continuation Phase.

m: All patients including those that discontinue protocol therapy will be followed for 3 years from the time of randomization. Patients that have not progressed during the Induction or Continuation Phase will continue to have imaging scans completed every 12 weeks, +/- 1 week (every 3 months) until documented progression.

n: PFTs with DLCO as medically indicated only, (PFTs are not otherwise required during course of study).

o: Follow every 3 months for disease progression and survival. Initiation of any new systemic therapy will also be documented.

* Cycle 1, Day 1 is defined as the first day on which fulvestrant is given in combination with placebo/everolimus (the second fulvestrant dose is given on day 15 of the first cycle only). Day 1 of each additional cycle is defined as the day in which fulvestrant is given in combination with everolimus/placebo.

^ End of Induction/End of Treatment should be performed within 30 days of last dose of fulvestrant.

£ Continuation Phase: Patients in the Continuation Phase should continue to receive fulvestrant alone (if originally randomized to placebo) or in combination with everolimus (if originally randomized to everolimus) at the same dose and schedule (+/- 1 week window for scheduled therapy/tests/visits; delays due to holidays, weekends, bad weather or other unforeseen circumstances will be permitted) until disease progression or unacceptable toxicity.

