#### **4.4. Dose Modifications and Toxicity Management**

Dose modifications for all drugs will be made using the general guidelines included in Protocol Section 5 (Tables 5-0, 5-1 and 5-2) and summarized below:

- All dose reductions are permanent. Fulvestrant will not be dose reduced.
- Regardless of the reason for holding any study drug treatment, the maximum allowable length of treatment interruption is  $\leq$  3 weeks. If the delivery of any study drug due to toxicity is delayed for more than 3 weeks, that drug should be permanently discontinued.
- No more than 2 dose reductions for everolimus/placebo will be allowed. Further need for dose reduction will result in discontinuation of that drug.
- If dose is delayed due to toxicity, labs/toxicity should be reevaluated at least weekly until recovery to treatment levels, or as indicated in the dose modification tables.
- Subjects who discontinue everolimus/placebo because of suspected everolimus-associated toxicity should continue treatment with fulvestrant alone until disease progression.
- In unusual circumstances where fulvestrant must be discontinued prior to disease progression due to intolerable fulvestrant-associated toxicity, the Medical Monitor should be contacted.

All toxicities will be graded according to the National Cancer Institute Common Terminology Criteria for Adverse Events (CTCAE), Version 4.0.

Toxicity management is defined in Section 5 of the protocol.

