#### **7.3.2. Case Status**

Number and percentage of subjects enrolled and ineligible will be summarized overall. Number of randomized subjects, withdrawn before treatment, eligible and treated will be summarized by randomized treatment arm. Percentages for ineligible will be based on all enrolled. Percentages for randomized subjects are based on all enrolled. Percentages for withdrawn before treatment, eligible and treated will be based on the number randomized within each treatment arm.

Number and percentage of subjects who completed Induction phase, discontinued during induction phase, were unblinded during induction phase, continued in Continuation phase, completed study, and discontinued the study will be summarized by treatment arm and overall. Percentages are based on number of eligible and treated subjects.

Subject's reasons for discontinuation at the end of treatment will be summarized by the following categories: adverse events, death, progressive disease, symptomatic progression, physician decision, protocol non-compliance, withdrawal by subjects, study terminated by sponsor, or unknown. If there are still subjects on treatment at the time the clinical study report is prepared, an additional category "Remain on treatment" will be included. Percentages will be calculated based on number of eligible and treated subjects.

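### SAP 7.3.2 and 7.5 give one undivided reason off treatment for a two-drug regimen, so no listed table shows when or why everolimus/placebo was stopped in patients kept on fulvestrant

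*SAP*

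**What the plan says.** On cycles, SAP 7.5 says: "The number of cycles of treatment received will be summarized by reason off treatment for all subjects evaluable for toxicity by treatment arm". Its worked rule is that someone who discontinues in cycle 5 is shown as having completed cycles 1 to 4, with the reason off treatment entered at cycle 5. SAP 7.3.2 says that a subject's "reasons for discontinuation at the end of treatment will be summarized by the following categories: adverse events, death, progressive disease", followed by symptomatic progression, physician decision, subject withdrawal and others, with an extra category for anyone still on treatment. Neither section says which drug the reason refers to.

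The regimen, however, is stopped one drug at a time. Protocol 5.3.1: "Patients who discontinue everolimus/placebo because of suspected everolimus-associated toxicity should continue treatment with fulvestrant alone until disease progression". Protocol 5.5 and SAP 4.3 and 4.4 repeat the rule. The footnote to the study table in Protocol Section 7 ties the closing visit to the other drug: "End of Induction/End of Treatment should be performed within 30 days of last dose of fulvestrant". Protocol 7.1.3 does the same.

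In SAP Appendix 1, Table 6 (cycles by reason off treatment) is by arm only. Table 7 (dosing) is the one output listed by arm and agent. For its average, SAP 7.5 says: "Dosing interval is the interval between the date of the first dose in the phase till the last dose date recorded in the diary". Days marked missed or withdrawn inside that interval count as 0 mg. Days after its end are not counted.

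Some toxicity stops follow a different route. Two rows of Protocol Table 5-1 (intolerable grade 2 mucositis, and grade 3 events with listed exceptions) withdraw the patient from the study if recovery takes longer than 21 days. Protocol 5.6 and SAP 4.5 also withdraw patients for an adverse event when the investigator judges this to be in their interest.

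**The concern.** Protocol 1.1 says that the study examines the efficacy and tolerability of the combination, and describing the safety profile is a secondary objective. How often the blinded drug is given up for toxicity, and when, is a direct measure of tolerability. The protocol itself reports it for everolimus in 5.3.2: "The rates of treatment-emergent adverse reactions resulting in permanent discontinuation were 7% and 0% for the everolimus and placebo treatment groups, respectively".

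The tables named in the SAP cannot produce that statistic. A patient who gives up everolimus early and stays on fulvestrant looks like someone still on full treatment until fulvestrant ends. If such stops are commoner with everolimus than with placebo, as in the renal cell study behind the 7% and 0%, the hidden stops fall mainly in the everolimus arm and its tolerability looks better than it was. What is at stake is the tolerability account in the publication, not the efficacy test.

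**Working it through.** **1. How one patient is tabulated.** Suppose a patient stops everolimus for toxicity in cycle 2, stays on fulvestrant under Protocol 5.3.1, and progresses in cycle 6.

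- SAP 7.5, Table 6: cycles 1 to 5 completed; off treatment in cycle 6 for progressive disease.
- SAP 7.3.2: reason at end of treatment is progressive disease.
- Nothing in either output records cycle 2 or the toxicity as the reason that everolimus ended.

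This takes off treatment to mean that both drugs have ended. The SAP does not define the term. The reading is supported by the fulvestrant-timed visit and by Protocol 5.5 and SAP 4.3, which describe discontinued induction therapy as fulvestrant together with everolimus/placebo.

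**2. Whether the dosing table reveals the stop.** The starting dose is 10 mg daily (Protocol 5.2.2) and a cycle is 28 days.

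| Course | SAP 7.5 average | Average over time on any protocol therapy |
|---|---|---|
| 1 cycle at 10 mg, then fulvestrant alone to day 168 | 280/28 = 10.0 mg | 280/168 = 1.7 mg/day |
| 1 cycle at 10 mg, then fulvestrant alone to day 336 | 280/28 = 10.0 mg | 280/336 = 0.83 mg/day |
| 3 cycles at 10 mg, then fulvestrant alone to day 336 | 840/84 = 10.0 mg | 840/336 = 2.5 mg/day |
| 1 cycle at 10 mg, 1 cycle at 5 mg, then fulvestrant alone to day 168 | (280 + 140)/56 = 7.5 mg | 420/168 = 2.5 mg/day |

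The last row uses Dose Level -1 from Table 5-0. An earlier reduction lowers the SAP average, but the days after the permanent stop are still not counted.

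**3. Other listed outputs.** Tables 8 to 11 give adverse events by grade and attribution, not the action taken on study drug. Listings 3 and 4 cover serious and grade 5 events. None is specified to give discontinuation of everolimus/placebo by reason and timing.

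**4. How many patients.** Protocol 9.2 assumes 65 treated per arm. Its own figures reproduce on that basis:

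- Chance of seeing at least one event with a true rate of 5%: 1 − 0.95^65 = 0.964, against 96% stated.
- Largest exact 90% interval width at n = 65: 21.6%, against 22% stated.

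The documents give no discontinuation rate for this regimen. Using the renal cell figure of 7% as an illustration:

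- Expected stops for an adverse event: 65 × 0.07 = 4.55, about 4.6 patients.
- If none stay on fulvestrant, all 4.6 appear under adverse events in the end-of-treatment table.
- If half stay, 4.55 × 0.5 = 2.3 appear (3.5% of 65).
- If all stay and none ends fulvestrant for an adverse event, 0 appear.

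Over an assumed range of 5% to 30%, the stops number 65 × 0.05 = 3.25 to 65 × 0.30 = 19.5, again with none to all hidden.

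**5. What does not move.** No input to the PFS design (5.4 versus 9.2 months, one-sided 10% alpha, 90% power, 98 events) depends on how discontinuation is tabulated.

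**The case against.** A reader might infer that everolimus stopped for adverse events will be reported as progression, and that the tables will show adverse-event discontinuation near zero. The documents do not support that, for these reasons:

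- **Withdrawal routes.** Patients withdrawn under the two Table 5-1 rows, Protocol 5.6 or SAP 4.5 leave all therapy and would fall under adverse events in SAP 7.3.2. Those rows conflict with the continue-fulvestrant rule in Protocol 5.3.1. Until they are reconciled, the share hidden cannot be known.
- **Other end reasons.** A patient kept on fulvestrant may finish through death, symptomatic progression, physician decision or withdrawal, or still be on treatment.
- **Undefined term.** The SAP names the End of Treatment CRF as the source of the reason only in 7.3.4, for subjects who never started. Reading off treatment as the end of both drugs is an inference.
- **Unseen templates.** Table detail is in a separate template document that is not available here. Appendix 1 mentions an additional adverse-event table in it, with contents unknown.
- **Dose average.** Many toxicities pass through interruption or reduction before a permanent stop, and these lower the Table 7 average. A stopper showing the full 10.0 mg is the extreme case.
- **The 7%.** It comes from a renal cell study, not from an assumption made for this trial.
- **Events are still reported.** The toxicity itself appears in the adverse-event tables, and the safety comparison is descriptive.

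All of this limits the size of the problem and rules out the stronger reading. It does not supply the missing output. The undefined term is itself a reason to act, since two programmers could build different tables from the same text. If the unseen template already covers discontinuation by drug, the SAP should say so.

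**Conclusion.** The point holds in a limited form. For patients who stop everolimus/placebo for toxicity and continue fulvestrant, SAP 7.3.2 and 7.5 give one reason off treatment, most naturally the reason that fulvestrant ended, and count fulvestrant-only cycles as completed. Table 7 leaves out the days after the stop. No output listed in the SAP or Appendix 1 gives everolimus/placebo discontinuation by reason and timing.

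About 4.6 of 65 everolimus patients are at issue at the illustrative 7%, and anywhere from none to all of them would be hidden. This rests on three assumptions: 65 treated per arm, a rate borrowed from another disease, and off treatment meaning both drugs. A bias favouring everolimus is plausible but cannot be sized from the documents.

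This is a cheap improvement to tolerability reporting. The PFS test, alpha and sample size are unaffected.

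**What to change.** In SAP 7.3.2, 7.5 and Appendix 1:

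1. Define off treatment separately for everolimus/placebo and for fulvestrant, and state which one each table uses.
2. Add a by-arm table, for all treated subjects, of permanent everolimus/placebo discontinuation: number, percentage, cycle and reason.
3. Add to Table 7 an average everolimus/placebo dose over Induction time on any protocol therapy, with days after permanent discontinuation counted as 0 mg. Keep the existing average beside it.

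Separately, the sponsor should reconcile the withdrawal rows of Table 5-1 with the continue-fulvestrant rule in Protocol 5.3.1, because the answer decides which patients reach which category.

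The cost is SAP and table-shell wording plus minor programming. The data should exist: Protocol 5.2.2 asks for dose changes and reasons to be recorded, and Protocol 5.3.2.8 (after Table 5-6) says "All interruptions or changes to study drug administration must be recorded". The downside for the sponsor is that the dose and discontinuation figures may look less favourable.

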## 7.6. Concomitant Medications

A by-subject data listing of bone modifying medications will be prepared for all treated subjects.

## 7.7. Efficacy Analysis

### 7.7.1. Response Analysis

Best overall response at the end of treatment will be summarized by treatment arm for all eligible, treated subjects. The summary table will include counts and percentages for each response category (CR, PR, SD, PD, unevaluable).

Objective response rate (defined as CR or PR among subjects with measurable disease) and clinical benefit rate (defined as CR, PR or SD for at least 24 weeks for subjects with measurable disease and as freedom from new lesions or unequivocal progression for at least 24 weeks among subjects with bone metastases only) will be estimated (n, %) for all eligible, treated subjects by treatment arm and disease stratum. The 90% exact binomial confidence interval for each of the three rates:

- Objective Response – Subjects with Measurable Disease
- Clinical Benefit – Subjects with Measurable Disease
- Clinical Benefit – Subjects with Bone Metastases Only

will also be included in the summary table. In the unlikely event that complete responses are observed among patients with bone metastases only, these will be described.

A by-subject data listing will be prepared to indicate the reason subjects were not evaluable for response. Include in this list subjects with:

- No re-evaluation of disease with Reason Unevaluable = No Re-evaluation of Disease. If subject discontinued study early, include reason for early termination in “Specify” column. If assessments were noted as “Not Done” at the time points/ visits prior to discontinuation, list visits when ‘not done’ and reason not done (one entry per time point).
- Re-evaluation of disease not done within required time frame
- Incomplete evaluation of disease (e.g., missing some target lesions that were evaluated at baseline).

